Several correlative studies have been built into the original protocol. The statistical considerations for the current study are slightly different, as we plan to incorporate a testing and validation cohort. We expect that 395 patients will have usable lymph node samples as specified in the protocol (assuming that tissue is available for 70% of study participants). The testing cohort will be comprised of the first half of these patients, or approximately 200 patients, and the results from the second 200 patients will be used for validating the results. On a case by case basis, some patients who are found to be ineligible for the clinical trial due to reasons other than pathology may be used for these analyses.

The underlying hypothesis for the correlative studies associated with this aim is that biomarker expression levels (i.e., (CD15, pSTAT3, VEGFR1 and CD68 cell counts in the benign nodal tissue) may predict clinical outcome (i.e., DFS). For each biomarker, recursive partitioning will be used to determine the cutoff value of average cell count that maximally distinguishes DFS within the training cohort. These cutoffs will be examined in the validation cohort.

[Table 1](#) provides an estimate of the minimally detectable hazard ratio for DFS for those with an elevated biomarker expression level (i.e., high CD15

	Prevalence of "High" Biomarker Expression Level				
	10%	20%	30%	40%	50%
DFS HR	2.40	1.93	1.80	1.74	1.73

Table 1. Minimally detectable hazard ratio (HR) for DFS for those with "high" biomarker expression versus those with "low" biomarker expression. Assuming 80% statistical power, 2-sided alpha of 0.05, and 200 patients in the training set (same power for the 200 patients in the validation set).

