expression) relative those with a low biomarker expression level. These effect sizes apply equally to the training and validation subsets since the sample size will be the same for both. The designation of "high" and "low" biomarker expression levels will be based on the cutoffs designated in the training cohort. These calculations assume 5 years of accrual, 3 additional years of follow-up, median 3-year DFS of 50% in those with "high" biomarker expression, a two-sided alpha of 0.05, and 80% statistical power. These calculations further assume that there is no interaction between the marker of interest and the randomized treatment assignment (type of lymph node dissection). Because all currently enrolling patients are being offered participation in the banking of their lymph node tissue, there will be no loss of sample size for this recently activated trial.

In some cases, there may be a combination of biomarkers that have a multiplicative effect on the risk of relapse. Classification and regression trees to assess the potential multiplicative effect amongst markers and form prognostic groups based on these algorithms will be explored. Prognostic models using traditional clinical factors such as clinical stage,

pathologic stage, age, receipt of neoadjuvant chemotherapy and performance status to predict disease-free survival will be developed in the training set and the area under the curve (AUC) will be calculated in the validation set. (43) Then, the model that also incorporates markers of the pre-metastatic niche (identified in the training set) will also be added to the model and the AUC will again be estimated. A comparison of the traditional AUC to the niche AUC will be made to evaluate whether these biomarker expression factors contribute to the DFS prognosis in this patient population.

Bibliography for 18.2

- 1 Fidler, I.J., Critical factors in the biology of human cancer metastasis: twenty-eighth G.H.A. Clowes memorial award lecture. *Cancer Res* 50(19):6130-8, 1990.)

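### Section 18.2b gives 80% power and alpha 0.05 equally to the training and validation halves because they are the same size; events differ between the halves, and the training alpha is not 0.05

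*Combined protocol and SAP*

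**What the plan says.** Appendix 18.2b (Statistical Plan) expects 395 usable lymph-node samples and divides them in two. One part is defined thus: "The testing cohort will be comprised of the first half of these patients, or approximately 200 patients". The other part serves as the check, in that "the results from the second 200 patients will be used for validating the results". The section calls the first half both the testing and the training cohort. For each of four markers (CD15, pSTAT3, VEGFR1, CD68), the cutoff comes from the training half: "recursive partitioning will be used to determine the cutoff value of average cell count that maximally distinguishes DFS". That cutoff is later applied to the validation half.

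Table 1 of that section lists detectable DFS hazard ratios of 2.40, 1.93, 1.80, 1.74 and 1.73 for a high-marker prevalence of 10, 20, 30, 40 and 50%. Its caption reads: "Assuming 80% statistical power, 2-sided alpha of 0.05, and 200 patients in the training set (same power for the 200 patients in the validation set". The text gives one reason for treating the halves alike: "These effect sizes apply equally to the training and validation subsets since the sample size will be the same for both". The stated assumptions are 5 years of accrual, 3 more years of follow-up and 3-year DFS of 50% in the high group. Section 7.7 limits follow-up to 6 years per patient.

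**The concern.** Equal numbers of patients give equal power for a time-to-event endpoint only if follow-up is also equal. A split into the first half and the second 200 reads most naturally as enrolment order. With a single analysis date, the later patients then have shorter follow-up and fewer events, and they form the half that has to confirm the markers.

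The caption also gives a fixed-cutpoint alpha to the training patients, although the training cutoff is selected on the same DFS data. An ordinary test at that cutoff is a maximally selected statistic and rejects a true null far more often than 5%. A reader who relies on the caption would give a training p-value below 0.05 more weight than it can bear.

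**Working it through.** **Inputs.** From 18.2b: 200 patients per half, the five prevalences and hazard ratios, two-sided alpha 0.05, and 5 + 3 years. High-group hazard λ₁ = ln 2/3 = 0.231 per year; low-group hazard λ₀ = λ₁/HR. From 7.7: 6-year limit. Assumed: split by enrolment order, uniform accrual, exponential DFS, no dropout, one analysis 3 years after accrual ends. Training patients (years 0-2.5) then have 5.5-8 years of potential follow-up, cut to 5.5-6 by the limit. Validation patients have 3-5.5 years.

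**The plan's own row.** No single formula tried reproduces the whole row from 3-8 years of follow-up. With variance 1/d₁ + 1/d₀ for the log hazard ratio (d₁, d₀ = expected events in the high and low groups), 3-8 years gives 2.25/1.85/1.72/1.67/1.67. With 3-5.5 years, the validation half's follow-up, it gives 2.40/1.94/1.80/1.75/1.75, within 0.02 of every printed value. So does 2-7 years, so the match does not show which calculation was made.

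**Events.** Expected events = Σ n_g × mean of [1 − exp(−λ_g t)] over the follow-up distribution. Example at 10% prevalence, HR 2.40 (20 high, 180 low; λ₀ = 0.0963):

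- Validation, t uniform on 3-5.5: event probabilities 0.620 and 0.334, so 20 × 0.620 + 180 × 0.334 ≈ 12.4 + 60.2 = 72.6.
- Training, 20% of patients uniform on 5.5-6 and 80% at 6 years: 0.747 and 0.436, so 20 × 0.747 + 180 × 0.436 ≈ 14.9 + 78.5 = 93.4.
- Deficit: 1 − 72.6/93.4 = 22%.

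**Power.** Power ≈ Φ(ln HR/√(1/d₁ + 1/d₀) − 1.96). For the same example, validation gives 0.875/√(1/12.4 + 1/60.2) = 2.81, so Φ(0.85) = 80%. Training gives 0.875/√(1/14.9 + 1/78.5) = 3.10, so Φ(1.14) = 87%. Log-rank simulation (20,000 runs per cell, cutoff fixed in advance):

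| Prevalence | HR | Training events | Validation events | Deficit | Training power | Validation power |
|---|---|---|---|---|---|---|
| 10% | 2.40 | 93.4 | 72.6 | 22% | 85.5% | 77.4% |
| 20% | 1.93 | 111.4 | 88.3 | 21% | 85.6% | 78.2% |
| 30% | 1.80 | 119.5 | 95.8 | 20% | 87.3% | 79.7% |
| 40% | 1.74 | 125.3 | 101.1 | 19% | 87.2% | 79.3% |
| 50% | 1.73 | 129.6 | 105.1 | 19% | 87.3% | 79.8% |

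A separate simulation put training at 84-87%. Without the 6-year limit, training has 101-138 events and 87-89% power; validation is unchanged.

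**Later analysis.** By the same formula without the follow-up limit, power at the tabled hazard ratios is 92-93% against 87-88% at 5 additional years, and about 93% against 90% at 6. If every patient reached the same 6 years, the gap would disappear.

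**Training alpha.** Null simulation: 200 patients, marker unrelated to DFS, largest |log-rank z| over all cutoffs searched, compared with 1.96. The search range is an assumption, because the plan gives none.

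| Cutoffs searched | Per-marker false-positive rate |
|---|---|
| The five tabled prevalences only | 16% |
| Deciles, 10-90 | 26% |
| All, 25th-75th centile | 28-30% |
| All, 20th-80th | 34% |
| All, 10th-90th | 44-45% |
| All, 5th-95th | 53% |

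A single pre-fixed median cutoff returned 5.0% in the same set-up. That is the situation in validation.

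**The case against.** The strongest reply is that the half carrying the inference is sized almost as printed. Validation power falls short of 80% by at most about 3 points, and its detectable hazard ratios agree with the printed row to within 0.02. The imbalance mainly means that training has more than the nominal power. For an average set of 200 patients followed 3-8 years, simulated power is 83-86%, so the table is mildly conservative. This stands. A reader might infer that the table materially overstates validation power; the figures do not support that. Schoenfeld's approximation is more pessimistic for validation (61-80%, worst at 10% prevalence), but the log-rank simulation does not bear it out.

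It is also fair to say that the plan uses training to find cutoffs and validation to test them, so the design already guards against optimistic cutoffs. This stands too. A reader might infer that training inflation carries into validation; it does not, because the cutoff is fixed before the validation data are examined. Nor does it follow that training findings would be mostly noise: that depends on how many markers are truly prognostic, which is unknown.

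Finally, enrolment order is the natural reading but is not stated. The analysis date is also open: Section 15.0 makes the studies wait for funding, and a later date narrows the power gap. Both limit the size of the first part of the point. Neither makes equal sample size a valid reason for equal power, and neither affects the training alpha.

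**Conclusion.** The point holds as a statement that is wrong as written, with modest consequences. Under an order-based split, 5 + 3 years, uniform accrual, exponential DFS and the 6-year limit, validation has about 19-22% fewer events. Its power is about 77-80%, against about 84-87% in training before cutoff selection.

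Alpha 0.05 does not describe an uncorrected training test at the selected cutoff. No single inflated figure can be put in its place: roughly 16-53% per marker is a range over assumed searches, and any one value in it is an illustration. Compounding it over four markers as if they were independent is not supported either, since 18.2b itself reports co-localization of VEGFR1 with CD68 macrophages and a possible role of pSTAT3 in neutrophil recruitment.

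Validation alpha stays at 0.05 per marker. The primary DFS comparison and the conduct of the trial are unaffected.

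**What to change.** In 18.2b, delete the sentence that applies the effect sizes equally and the same-power note in the Table 1 caption. State instead that two-sided alpha 0.05 and the tabled hazard ratios refer to the pre-fixed cutoff in the validation half. If the order-based split is kept, give power there as about 77-80% at 3 additional years of follow-up. Say explicitly that the halves are defined by enrolment order, and give the planned analysis date. Report training results without p-values, or with a maximally selected log-rank correction and a stated cutoff search range.

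The cost is wording only. A random split would equalise expected follow-up (simulated power about 82-85% in each half with the 6-year limit), but it gives up the temporal element of the validation. It is an option, not a needed correction.

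### Section 18.2b judges the added value of the niche markers only by an unspecified AUC comparison in about 200 validation patients, and Table 1's 80% power does not carry over to it

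*Combined protocol and SAP*

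**What the plan says.** Section 18.2b (Statistical Plan) splits about 395 patients with usable nodal tissue into two halves. The first half is used to find marker cutoffs; for the rest, "the results from the second 200 patients will be used for validating the results".

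Three analyses follow.

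- **Cutoffs.** A cutoff for each of CD15, pSTAT3, VEGFR1 and CD68 is found in the first half and examined in the second. No adjustment for clinical factors is mentioned.
- **Table 1 of 18.2b.** This gives detectable DFS hazard ratios of 2.40, 1.93, 1.80, 1.74 and 1.73 at prevalences of 10, 20, 30, 40 and 50%. The caption reads "Assuming 80% statistical power, 2-sided alpha of 0.05, and 200 patients in the training set", and the text adds "These effect sizes apply equally to the training and validation subsets since the sample size will be the same for both".
- **Added value.** A model using clinical and pathologic stage, age, neoadjuvant treatment and performance status is developed in training, and "the area under the curve (AUC) will be calculated in the validation set". Niche markers are then added and the AUC is estimated again. The criterion is "A comparison of the traditional AUC to the niche AUC will be made to evaluate whether these biomarker expression factors contribute".

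For the third analysis the plan states no test, alpha, time point, handling of censoring, target gain or power. The reference cited at that step is number 43, but the 18.2 bibliography ends at 25 and the main one at 30.

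**The concern.** Table 1 and the AUC step answer different questions. Table 1 asks whether DFS differs between high- and low-expression patients. The AUC step asks whether markers improve discrimination once clinical factors are in the model. A covariate with a clear hazard ratio can move the AUC of an already informative model very little, so comparing nested AUCs is an insensitive way to detect added value.

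A reader who sees 80% power and equal effect sizes for the validation set may take an unimpressive AUC difference as evidence that the markers add nothing. If the comparison has low power, that inference fails, although the same 200 patients could support a more sensitive test.

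**Working it through.** **Inputs from 18.2b.** Validation n = 200; two-sided alpha 0.05; the Table 1 hazard ratios; "These calculations assume 5 years of accrual, 3 additional years of follow-up"; and "median 3-year DFS of 50% in those with" high expression, that is, a median of 3 years. **Assumed, because the plan is silent:** clinical-model AUC, time point, test, number of markers, and marker-clinical correlation (zero unless stated).

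**1. Reproduce Table 1.** With exponential DFS and uniform accrual, the event probability is P(λ) = 1 − [e^(−3λ) − e^(−8λ)]/(5λ). Take prevalence 30% and HR 1.80.

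- High group: λ = ln2/3 = 0.2310, P = 0.7035, events 60 × 0.7035 = 42.2.
- Low group: λ = 0.2310/1.80 = 0.1284, P = 0.4979, events 140 × 0.4979 = 69.7.
- SE of log HR = √(1/42.2 + 1/69.7) = 0.195.
- Power = Φ(ln 1.80/0.195 − 1.96) = Φ(3.01 − 1.96) = 0.85.

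Solved for the hazard ratio across prevalences, this formula gives 2.25/1.85/1.72/1.67/1.67 at 80% power and 2.39/1.94/1.79/1.74/1.73 at 85%. The stated values match the 85% row to within 0.01. Simulated log-rank power at the stated values is 82-86%. Table 1 is therefore slightly conservative. It contains no clinical covariate and no AUC.

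**2. Simulate the AUC step.** Each replicate has 200 training and 200 validation patients. Log-hazard = ln(HR)·(marker − 1) + s·(standard normal clinical score), baseline hazard ln2/3, censoring uniform on 3 to 8 years. Cox models are fitted in training and their scores carried to validation. The AUCs for 3-year DFS status are compared by DeLong (z > 1.96 in favor of the marker). The alternative is the Wald test of the marker in a validation Cox model containing the clinical score. There were 2,000 replicates per setting; ranges run over the five Table 1 rows.

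| s | Clinical AUC | AUC gain | 3-year AUC test | 5-year AUC test | C-index test | Adjusted Cox |
|---|---|---|---|---|---|---|
| 0.25 | 0.58-0.59 | 0.037-0.042 | 21-26% | 26-32% | 30-32% | 82-85% |
| 0.45 | 0.64-0.65 | 0.023-0.025 | 16-22% | 21-24% | 22-26% | 82-85% |
| 0.65 | 0.70-0.71 | 0.016-0.017 | 14-21% | 19-21% | 20-25% | 81-84% |
| 0.90 | 0.76-0.77 | 0.011-0.012 | 13-18% | 16-18% | 18-23% | 80-84% |

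A separate simulation with clinical AUC 0.60-0.79 gave 13-29% for the 3-year AUC comparison and 79-89% for the Cox term.

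**3. Why the gap is so large.** At 30% prevalence, HR 1.80 and s = 0.65, power is 18.8% for the 3-year AUC and 84.4% for Cox. On a rough normal scale the expected z is 1.96 + Φ⁻¹(0.188) = 1.96 − 0.89 = 1.07 for the AUC gain and 1.96 + Φ⁻¹(0.844) = 1.96 + 1.01 = 2.97 for the Cox term. With HR 1.00 at 30% prevalence, z > 1.96 occurs in 0.8% of AUC comparisons and 2.9% of Cox tests, against a nominal 2.5%, so the AUC comparison is also conservative under the null.

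**4. Vary the open choices.**

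- A smaller run (600 replicates, clinical AUC 0.63-0.79): 9-23%.
- Four noise covariates added to the clinical model: 15-33% at 3 years, and 22-41% at 5 years ignoring censoring.
- Two markers each at the Table 1 HR: 35-42%. Four: 59-67% (clinical AUC about 0.65).
- Cohorts split by enrollment order, so that validation follow-up is about 3 to 5.5 years: AUC 15-24%, Cox 75-80%.
- Unadjusted HR held at 1.80 (30% prevalence) with the marker correlated with the clinical score: Cox power falls to 58-68% at correlation 0.2 and 10-35% at 0.4. AUC power would fall too.

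**The case against.** The strongest reply is that the plan claims no power for the AUC comparison, so no stated figure is wrong. That stands: the defect is an unspecified and insensitive criterion. Four stronger readings are tempting, and the documents do not support them.

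- **Power is under 20%.** That needs one marker, a 3-year AUC, a DeLong test and a fairly strong clinical model, none of which 18.2b fixes. The plan speaks of markers in the plural, and two to four full-strength markers would raise power to 35-67%. Four is optimistic: the 20-patient pilot in 18.2b saw no outcome difference for VEGFR1 (P=0.60) or CD68 (P=0.28).
- **The AUC ignores event times.** The text says only AUC. A time-dependent version that handles censoring is equally consistent with it.
- **The validation cohort fails its purpose.** Objective 1.3b is the prognostic value of the markers. Examining the training cutoffs in the validation cohort serves that objective and is what Table 1 sizes. Only the added-value question is affected.
- **A real marker would be reported as adding nothing.** This presumes a significance rule the plan does not state; the comparison could be an estimate with an interval.

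It can also be said that section 11.4 plans multivariable proportional hazards models. Its stated aim is the epithelial-mesenchymal transition markers, however, and 18.2b says its own considerations differ. For the niche markers' added value, the AUC comparison is the only analysis named.

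Finally, the 80-85% for Cox is a favorable benchmark. Table 1's hazard ratios are unadjusted, and correlation with stage or other clinical factors would erode it. This limits what the replacement can promise but does not restore the AUC comparison.

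**Conclusion.** The point holds as a minor one. Added value over clinical factors rests on a single unspecified AUC comparison to which Table 1's power does not apply. For one marker at the Table 1 hazard ratios, uncorrelated with the clinical score, that comparison has roughly 10-40% power, against about 80-85% for the adjusted Cox term in the same patients. The exact figure depends on the time point, the test, the clinical AUC and the number of markers. Even with four full-strength markers it stayed below 80% in the settings tried. A null AUC comparison would therefore say little about whether the markers add information.

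Severity is low: the aim is exploratory, the tissue is optional, section 15.0 makes the work conditional on funding, and the primary DFS analysis is untouched.

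**What to change.** In 18.2b, replace the AUC comparison as the criterion. In the validation set, fit a Cox model for DFS with the training-derived clinical score and the training-derived marker score (or cutoff), and let the test of the marker term, with its alpha stated, decide added value. Report the change in a time-dependent AUC that handles censoring, at a named time point, or in the C-index, with a confidence interval and as description only. State that Table 1 refers to unadjusted hazard ratios and that adjusted power will be lower if markers correlate with clinical factors.

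The cost is a few sentences and one extra model, with no new data. A hazard ratio is less intuitive than an AUC, which is why both are shown. Because the translational work awaits funding, the wording can be settled before any marker is measured.
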